3.1.3 Diagnostic and therapeutic methods of medical devices for investigation

All subjects used ProBeam, an investigational medical device. The investigator formulated an individualized radiotherapy plan according to the actual clinical situation of the subjects, and the use of experimental medical devices is detailed in the product manual.

The specific treatment process is: preoperative assessment to determine the indications (radiotherapist) → signing of the informed consent form for radiotherapy (radiotherapist) → selection and production of postural immobilization devices (radiotherapist, radiotherapist, physicist) → CT/MRI Simulation positioning (radiotherapist, radiotherapist, physicist) → target and normal organ delineation (radiotherapist) → radiotherapy plan design (physicist) → radiotherapy plan review and authorization for executable plans (radiotherapist, physicist), → treatment plan validation (physicist), → proton radiation therapy (radiotherapist). First treatment, radiotherapist and physicist are present) → post-treatment efficacy evaluation (radiotherapist, independent imaging review team) → follow-up (radiotherapist).

Subjects will receive radiotherapy with reference to the dose and segmentation prescribed by the trial, and the expected radiotherapy cycle of each subject is 1~8 weeks.

3.1.3.1 Enrollment time

The investigators obtained the informed consent of the participants and signed the ICF, which was then screened according to the inclusion criteria. If the patient meets all the inclusion criteria of this trial and does not meet any of the exclusion criteria, the case is included in this trial, and the time of enrollment of the subject is used as the treatment on the day of the first treatment, and a unique enrollment number is obtained in the order of enrollment.

3.1.3.2 The number of subjects required for the clinical trial

After screening according to the inclusion criteria, it is expected that a total of 47 subjects will be included in this clinical trial, all of whom will be treated with investigational medical devices.

3.1.4 Effectiveness evaluation methods

If it is not possible to follow up at the clinical trial center according to the visit arrangement due to the epidemic, the clinical examination can be examined by other tertiary hospitals, and the test results will be transmitted back to the clinical trial center for evaluation; The carrier of imaging data in the outer hospital is not limited, and it is necessary to ensure that the imaging department of the center can be opened and read.

3.1.4.1 The main effectiveness evaluation indicators and the methods and time selection of their evaluation, recording and analysis

(1) Tumor disease control rate (DCR).

Reason for selection: According to the clinical trial effectiveness evaluation in the "Guidelines for the Review of Clinical Evaluation Technologies of Proton Carbon Ion Therapy System" (CFDA Circular No. 4 [2018]): "In view of the local characteristics of radiotherapy, it is recommended that the efficacy evaluation should be based on local control, and according to

the different diseases, the common standards in clinical research, such as the efficacy evaluation criteria for solid tumors, should be reasonably adopted RECIST. The efficacy evaluation can be divided into complete response CR, partial response PR, disease stable SD, disease progression PD, and the effective definition is: "CR+PR+SD.""; Due to the particularity of the disease, the evaluation method recommended in the relevant diagnosis and treatment guidelines is selected. The tumor disease control rate was selected as the main effectiveness evaluation index, which was relatively objective and reproducible, and adopted the common standard in clinical research, which was widely recognized and applied by clinicians.

Definition of indicators: the occurrence of CR, PR and SD after the end of treatment is disease control; No biochemical recurrence at the end of prostate cancer treatment, no regional lymph nodes or distant metastases, considered disease control. Proportion of participants who developed disease control three months after the end of the last radiotherapy.

Metric type: Qualitative.

Data collection time: screening period, 3 months \pm 7 days after the end of the last treatment.

Evaluation time: 3 months \pm 7 days after the end of the last treatment.

Site of evaluation: Tumor receiving radiation therapy.

Evaluation method: The changes in tumor CT or MRI imaging before and after treatment were evaluated by an independent imaging review panel according to RECIST 1.1. At 3 months of radiographic evaluation, if PD is found, PET-CT is required to confirm it.

Calculation formula: DCR = number of disease control subjects / total number of subjects \times 100%.

Criteria: See RECIST 1.1 for details. At the time of 3-month imaging evaluation, if the patient is found to have PD, PET-CT examination is required to confirm it, if progress is confirmed, it is recorded as PD, if progress cannot be confirmed, it may

be false progression, and it is recorded as SD. If prostate cancer does not have biochemical recurrence, PET-CT examination is not required, and there is no metastasis by default, which is regarded as tumor control, and if biochemical recurrence occurs, it is regarded as tumor not controlled, and PET-CT is required to confirm tumor metastasis.

Note: Participants who aborted the trial for any reason (except loss to follow-up) before the end of the last radiation therapy were considered to have disease progression (PD) or were not controlled. Disease site evaluation uses the same approach as baseline, including consistent contrasted/non-contrast scans and prompt scanning. If changes are needed, the case must be discussed with a radiologist to determine whether an alternative approach is possible. If not, the objective situation in the future is unclear.

3.1.4.2 Secondary effectiveness evaluation indicators and their methods and timing of evaluation, recording, analysis

(1) Objective response rate (ORR).

Reason for selection: The Guidelines for the Review of Clinical Evaluation Technologies of Proton Carbon Ion Therapy Systems (CFDA Circular No. 4 [2018]) recommends the use of the latest version of the commonly used evaluation criteria for radiation oncology as the clinical trial evaluation criteria, so RECIST 1.1 is used. Relevant indicators as effectiveness evaluation criteria; Due to the particularity of the disease, the evaluation method recommended in the relevant diagnosis and treatment guidelines is selected. All of them can directly measure the effect of radiotherapy and are widely recognized and applied by clinicians.

Definition of indicators: CR or PR after the end of treatment is considered objective remission, prostate cancer has no biochemical recurrence at the end of the last treatment, and no regional lymph nodes or distant metastasis are considered objective remission. Proportion of participants who experienced objective remission at each time point after the end of the last treatment.

Metric type: Qualitative.

Data collection time: screen period, 3 days, 1 month \pm 7 days, 2 months, \pm 7 days, 3 months, \pm 7 days after the end of the last treatment.

Evaluation time: 3 days, 1 month \pm 7 days, 2 months, \pm 7 days, 3 months, \pm 7 days after the last treatment.

Site of evaluation: Tumor receiving radiation therapy.

Evaluation method: The changes in tumor CT or MRI imaging before and after treatment were evaluated by an independent imaging review panel according to RECIST 1.1. At 3 months of radiographic evaluation, if PD is found, PET-CT is required to confirm it.

Calculation formula: ORR = number of subjects in objective response / total number of subjects \times 100%.

Criteria: See RECIST 1.1 for details. At the time of 3-month imaging evaluation, if the patient is found to have PD, PET-CT examination is required to confirm it, if progress is confirmed, it is recorded as PD, if progress cannot be confirmed, it may be false progression, and it is recorded as SD. If prostate cancer does not have biochemical recurrence, PET-CT examination is not required, and there is no metastasis by default, which is regarded as objective remission, and if biochemical recurrence occurs, it is regarded as not objectively remission, and PET-CT is required to confirm tumor metastasis.

Note: Participants who aborted the trial for any reason (other than loss to follow-up) before the end of the last radiotherapy were considered to have not responded objectively. Disease site evaluation uses the same approach as baseline, including consistent contrasted/non-contrast scans and prompt scanning. If changes are needed, the case must be discussed with a radiologist to determine whether an alternative approach is possible. If not, the objective situation in the future is unclear.

(2) Tumor disease control rate (DCR).

Reason for selection: DCR 3 months after the end of the last treatment was the primary evaluation index, and DCR at other follow-up time was used as a secondary evaluation index.

Definition of indicators: the occurrence of CR, PR and SD after the end of treatment is disease control; No biochemical recurrence at the end of prostate cancer treatment, no regional lymph nodes or distant metastases, considered disease control. Proportion of participants who developed disease control at one month after the end of the last treatment.

Metric type: Qualitative.

Data collection time: screen period, 3 days , 1 month \pm 7 days, 2 month \pm 7 days after the end of the last treatment.

Evaluation time: 3 days, 1 month \pm 7 days, 2 month \pm 7 days after the last treatment.

Site of evaluation: Tumor receiving radiation therapy.

Evaluation method: The changes in tumor CT or MRI imaging before and after treatment were evaluated by an independent imaging review panel according to RECIST 1.1. At 3 months of radiographic evaluation, if PD is found, PET-CT is required to confirm it.

Calculation formula: $DCR = \frac{\text{number of disease control subjects}}{\text{total number of subjects}} \times 100\%$.

Criteria: See RECIST 1.1 for details. At the time of 3-month imaging evaluation, if the patient is found to have PD, PET-CT examination is required to confirm it, if progress is confirmed, it is recorded as PD, if progress cannot be confirmed, it may be false progression, and it is recorded as SD. If prostate cancer does not have biochemical recurrence, PET-CT examination is not required, and there is no metastasis by default, which is regarded as tumor control, and if biochemical recurrence occurs, it is regarded as tumor not controlled, and PET-CT is required to confirm tumor metastasis.

Note: Participants who aborted the trial for any reason (other than loss to follow-up) before the end of the last radiotherapy were considered to have PD or was uncontrolled. Disease site evaluation uses the same approach as baseline, including consistent contrasted/non-contrast scans and prompt scanning. If changes are needed, the case must be discussed with a radiologist to determine whether an alternative approach is possible. If not, the objective situation in the future is unclear.

(3) Tumor markers (if needed)

Reason for selection: The Guidelines for the Review of Clinical Evaluation Technologies of Proton Carbon Ion Therapy System (CFDA Circular No. 4, 2018) suggests that changes in tumor markers and functional imaging parameters should be used as reference factors for effectiveness evaluation.

Data collection and evaluation time: screen period, 3 days, 1 month \pm 7 days, 2 months \pm 7 days, 3 months \pm 7 months after the end of the last treatment Sky.

Evaluation method: tumor marker examination is performed, and the investigator judges that the tumor marker (before and after radiotherapy) is reported as clinically significant changes.

Note: Researchers choose relevant indicators according to the disease, and the scheme is not uniformly stipulated.

(4) Product usability evaluation (ProBeam360 system, radiotherapy management software (Aria), radiotherapy planning software (Eclipse)).

Reason for selection: Routine effectiveness indicators of medical device clinical trials.

Indicator type: quantitative, open-ended question.

Data collection and evaluation time: the day the last treatment was completed.

Evaluation method: Researchers using the corresponding function scored according to the Likert scale and collected open-ended questions to evaluate the overall feeling of ease of use during treatment.

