The expected duration of the participant's participation	The screening period from signing the informed consent form to enrollment is expected to be 4 weeks, the treatment period is 1~8 weeks, and the follow-up after the last treatment are divided into short-term follow-up and long-term follow-up, and the maximum duration of expected participation of each subject from screening to the end of short-term follow-up is 12 weeks +3 months. Long-term follow-up continued after the end of the short-term follow-up until the fifth year after the end of the last radiotherapy. (After a 3-month follow-up after the last treatment, a "Medical Device Clinical Trial Report" will be issued for the registration of this trial

product Declaration.)

Expected overall duration of clinical trials and long-term follow-up	
The first subject is expected to be enrolled in June 2024, and the clinical trial institution expects to enroll 12 subjects per month, for a total enrollment time of about 4 months, and the last subject ends the trial (short-term follow-up) is In April 2025.
 
The last subject to end long-term follow-up in January 2030.

Primary effectiveness	
Disease Control Rate (DCR).
 
Evaluation time: 3 months \pm 7 days after the last treatment.
 
Definition of indicators: Complete Response (CR), Partial Response (PR), Stable Disease (SD) for disease control. Proportion of participants who developed disease control three months after the end of the last radiotherapy.

Evaluation indicators	
Evaluation methodology: Response Evaluation Criteria in Solid Tumors RECIST Version 1.1 (RECIST 1.1) by an independent imaging review team in tumour CT or MRI imaging before and after treatment were assessed.
 
Participants who discontinued the trial for any reason (except loss to follow-up) before the end of radiation therapy were considered to have not controlled.

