5.3.8 Concomitant therapy

A detailed description of the subject's concomitant treatment based on the FAS list.

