5.4 Effectiveness evaluation indicators

5.4.1 Key Effectiveness Indicators

The primary effectiveness evaluation was based on the Full Analysis Set (FAS) and the Protocol-Consistent Set (PPS).

The number and percentage of cases that achieved tumor disease control at 3 months during the follow-up period were calculated, and the 95% confidence interval of tumor disease control rate was calculated by Clopper-

Pearson, and the target value of tumor local control rate was 80%, and if the lower limit of the 95% confidence interval of the test results was greater than 80%, the tumor local control rate was reached. The single-sample chi-square test was used to compare whether there was a statistical difference between the local control rate and the target value.

For the evaluation results of the imaging review team, if the efficacy evaluation results of the two evaluators are consistent, the final evaluation results of the two evaluators will be taken, and if the evaluation results of the two evaluations are inconsistent, the independent evaluation value of the third evaluator will be taken as the final evaluation results.

Based on FAS, the sensitivity analysis of the main effectiveness indicators was carried out, and the missing values of the main effectiveness evaluation indicators were filled by the method of Worst Observational Data Carryover (WOCF).

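### The primary DCR has no scoring rule for a new anticancer treatment of the irradiated tumour between the last radiotherapy and month 3, so control achieved by that treatment is credited to ProBeam360

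*Protocol*

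**What the plan says.** **Endpoint.** Protocol 3.1.4.1 defines the primary DCR as "Proportion of participants who developed disease control three months after the end of the last radiotherapy". Data come from screening and from 3 months ± 7 days, and the site assessed is the irradiated tumour. SAP 5.4.1 follows this: "The number and percentage of cases that achieved tumor disease control at 3 months during the follow-up period were calculated".

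**The one overriding event.** The note in Protocol 3.1.4.1 treats "Participants who aborted the trial for any reason (except loss to follow-up) before the end of the last radiation therapy" as progressed or not controlled. The protocol summary sets the same cut-off: "Participants who discontinued the trial for any reason (except loss to follow-up) before the end of radiation therapy were considered to have not controlled". No corresponding rule covers the three months after radiotherapy.

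**Earlier readings.** Tumours are also assessed at 3 days, 1 month and 2 months, but Protocol 3.1.4.2 keeps these apart: "DCR at other follow-up time was used as a secondary evaluation index". Confirmation of progression is written for the endpoint visit: "At 3 months of radiographic evaluation, if PD is found, PET-CT is required to confirm it". Progression that cannot be confirmed there is recorded as SD.

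**Other treatment.** SAP 5.3.8 provides only a listing: "A detailed description of the subject's concomitant treatment based on the FAS list". Protocol 4.4 names use of prohibited concomitant medications or devices as a possible reason for being a dropout, meaning not included in the primary analysis. The PPS definition (Protocol 4.9, SAP section 3) does not mention new anticancer treatment.

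**Missing values.** Protocol 4.7.2 allows worst-case estimation of a missing month-3 DCR. SAP 5.4.1 fills missing values in FAS by carrying the worst observation forward (WOCF), while SAP 4.3 says they are not filled.

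**The concern.** The stated objective is whether ProBeam360 reaches the 80% target at 3 months. There is no control arm, so whatever produces control at month 3 is attributed to the device.

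Take a subject with PD of the irradiated tumour at month 1 who then has surgery or systemic therapy for it and shows CR, PR or SD at month 3. As written, that subject counts as controlled. The same holds for a subject who starts such treatment without a prior PD reading. The error can only run in the device's favour.

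The plan is also uneven. Under SAP 5.4.1, a subject with PD at month 1 and no month-3 scan would carry the PD forward as a failure in FAS. A subject with the same PD who is then treated and scanned can be a success.

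**Working it through.** **1. Does any rule catch the case?** The case is a new treatment of the irradiated tumour after radiotherapy, with an observed CR, PR or SD at month 3.

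| Provision | Effect on this subject |
|---|---|
| Early-withdrawal note (Protocol 3.1.4.1) | None: the event follows radiotherapy |
| Worst case or WOCF (Protocol 4.7.2, SAP 5.4.1) | None: month 3 is not missing |
| Dropout text (Protocol 4.4) | At most exclusion, not failure; the available text has no list of prohibited treatments |
| PET-CT confirmation | None: it is triggered by PD at month 3 |
| FAS sensitivity analysis (SAP 5.6) | None: it varies the population and missing-value filling, not the scoring |

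**2. The plan's own sample size.** Inputs: target p0 = 0.80, expected p1 = 0.95, two-sided alpha 0.05, power 80%, dropout 10% (protocol summary, Protocol 4.2).

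n = [(1.960·√(0.80·0.20) + 0.842·√(0.95·0.05)) / 0.15]² = 41.59, rounded up to 42. Then 42 / 0.90 = 46.7, rounded up to 47. Both figures reproduce.

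**3. Pass line.** Success requires a Clopper-Pearson two-sided 95% lower limit above 80% (Protocol 4.5, 4.7.1).

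| Controlled | Lower limit | Result |
|---|---|---|
| 39/42 | 80.5% | pass |
| 38/42 | 77.4% | fail |
| 44/47 | 82.5% | pass |
| 43/47 | 79.6% | fail |

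Three failures are allowed at either size. If one of 39 controlled subjects in 42 owes control to later treatment, scoring that subject as a failure gives 38/42 and a fail. Excluding the subject gives 38/41, lower limit 80.1%, still a pass. Exclusion is therefore not a substitute for a scoring rule.

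**4. Chance of a wrong pass.** Let m be the share of all subjects scored controlled only through later treatment. The documents do not give m; 0 to 10% is an assumed range. With true control at 80%, the pass probability is P(X ≥ 39), X ~ Bin(42, 0.80 + m), and for 47 subjects P(X ≥ 44), X ~ Bin(47, 0.80 + m).

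| m | n = 42 | n = 47 |
|---|---|---|
| 0 | 2.1% | 0.9% |
| 2% | 4.1% | 2.1% |
| 5% | 10.7% | 6.4% |
| 10% | 38.4% | 29.6% |

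**5. Power cost of the correction.** If 95% describes the endpoint as now scored, reclassifying a share m leaves a true rate of 0.95 − m. Power is P(X ≥ 39), X ~ Bin(42, 0.95 − m), and P(X ≥ 44), X ~ Bin(47, 0.95 − m).

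| m | n = 42 | n = 47 |
|---|---|---|
| 0 | 84.3% | 79.3% |
| 2% | 66.1% | 58.0% |
| 5% | 38.4% | 29.6% |

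With the formula of step 2, 80% power would need 60 evaluable (67 enrolled) at a true rate of 93%, and 108 (120 enrolled) at 90%.

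**The case against.** A reader might go further and infer that every subject with PD at month 1 or 2 who is SD or better at month 3 is wrongly scored. The documents do not support that. Without new treatment, such a course may be false progression. Protocol 3.1.4.1 recognises this at month 3 and records unconfirmed PD as SD, and no PET-CT confirmation is provided for the earlier scans. That objection stands, and early PD alone is outside this point.

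Other limits also stand:

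- Prostate subjects are judged on biochemical recurrence, which Protocol 3.1.4.1 already scores as not controlled.
- The endpoint is local. Systemic therapy begun for disease elsewhere is not evidence that the irradiated tumour was uncontrolled.
- That one subject can flip the result is true of any reclassification at a threshold. At the planned 95%, a count of exactly 39/42 has probability about 19%, and 44/47 about 21%.
- Eligibility requires expected survival beyond 6 months and excludes other uncontrolled tumours, so early new treatment may be uncommon.
- The 80% target is tied to a guideline definition of CR+PR+SD. A stricter endpoint is harder to pass against the same target.

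Partial handling exists too: early DCR is reported as a secondary endpoint, and deviations are reviewed before lock (SAP 5.3.2). Neither changes how an observed month-3 scan is scored. RECIST 1.1, to which the protocol refers, was not available for this review, so the point rests on the documents' own scoring text.

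**Conclusion.** The point holds for new, not pre-planned treatment of the irradiated tumour between the last radiotherapy and month 3, with or without an earlier PD. Followed as written, the scoring credits the result of that treatment to the device, and no other provision makes the subject a failure.

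Its size depends on a frequency the documents do not give. Under the assumptions of 80% true control and independent subjects, a 2% share about doubles the chance of passing at 42 evaluable subjects (2.1% to 4.1%) and a 5% share raises it about fivefold (to 10.7%). If the share is zero, nothing changes.

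The documents do not show that such cases will occur, that the trial will pass wrongly, or that all early PD must count as failure. The sample size arithmetic is not in dispute. This should be fixed before database lock, since a later choice could be made with the results known. A case for making every early PD a failure in the primary analysis is not established.

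**What to change.** In Protocol 3.1.4.1 and SAP 2.1.1 and 5.4.1:

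1. Score as not controlled, in both FAS and PPS, any subject who starts a new, not pre-planned treatment directed at the irradiated tumour before the month-3 assessment, whether or not PD was read earlier. Define what counts as pre-planned.
2. Flag systemic therapy started only for disease outside the irradiated site, and handle it in a sensitivity analysis.
3. Leave PD read by the panel at month 1 or 2 without new therapy scored by the month-3 reading, and add a sensitivity analysis that counts it as failure.
4. Keep the present month-3 snapshot as a supportive analysis.

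The drafting cost is a few sentences and a derived flag. Concomitant treatment and month-1 and month-2 imaging are already planned for collection, but the data must show start date, target and whether the treatment was pre-planned. The statistical cost is real: the DCR can only be equal or lower, and the power loss shown in the working should be stated in the sample size section. The change concerns scoring only, not the care that subjects may receive.

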ULN	Upper Limit of Normal	Upper limit of normal value
VMAT	Volumetric-Modulated Arc Therapy	Volumetric rotational intensity-modulated radiotherapy
WBC	White Blood Cell	white blood cell
WHO	World Health Organization	World Health Organization

Protocol summary

The name of the experiment	Varian ProBeam360 Proton Therapy System China Clinical Trial (Wuhan).
Device name	proton therapy system (hereinafter referred to as ProBeam360).
Manage categories	Class III (classification: 05 radiotherapy equipment--01 radiotherapy equipment--02 medical light ion therapy system).
Scope of application	Proton therapy system provide precision radiation therapy protons for lesions, tumors, and conditions in the patient's body that require radiation therapy.
Scope of the test	Cancer patients, including tumors of intracranial, head and neck, chest, abdomen, spine, pelvis, limbs, etc
Trial design	Prospective, open-label, single-centered, single-group target value method
Trial and long-term follow-up purposes	
Clinical trial (screening-short-term follow-up): The data obtained by using Proton Beam system (ProBeam360) for radiation therapy in tumor patients compared with the target value to evaluate the effectiveness and safety of ProBeam360 for radiation therapy in tumor patients to provide clinical basis for product registration application.
 
Long-term follow-up: The long-term efficacy and safety of ProBeam360 for radiation therapy in cancer patients were evaluated by using the long-term follow-up data of ProBeam360 for radiation therapy in cancer patients.

Sample size	
At least 47 participants are enrolled in this trial.
 
Assuming the expected primary efficacy evaluation indicator (3-month tumor local control rate) is 95%, the target value is 80%, the bilateral significance level is 0.05, and the confidence level is 80%, data from 42 participants are required at the end of the 3-month observation period.
 
Considering the expected dropout rate of 10% during short-term follow-up of clinical trials, 47 subjects are required to be enrolled.
 
(1) The number of cases of tumors in the intracranial, head and neck, chest, abdomen, spine, pelvic cavity, and limbs should be evenly distributed as much as possible.
 
(2) The Intensity Modulated Proton Therapy (IMPT) technology and exercise management system should be used and validated in this study.

clinical trial	
Number of institutions	1 site

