4.2 Sample size calculation

4.2.1 Total sample size

This clinical trial intends to enroll 47 subjects. The sample size determination process is as follows:

This clinical study is designed for clinical verification of a single group of target values, and the tumor disease control rate, the main effectiveness evaluation index, is used as the basis for sample size estimation. According to the Guidelines for the Review of Clinical Evaluation Technologies of Proton Carbon Ion Therapy System (CFDA Circular No. 4 of 2018), the target value is set at 80%, and the bilateral significance level is 0.05, and the power degree 80%, applying the sample size estimation professional software PASS 15.0, calculated by the above parameters, the test group needs a sample size of at least 42 cases. Considering that about 10% of cases may be dropped or lost to follow-up during clinical validation, the sample size of the experimental group was expanded to 47 cases.

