4.3 The level of significance and power of clinical trials

The significance level α (bilateral) = 0.05, and the power was 80%.

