4.3 Effectiveness indicators are missing

When analyzing the main effectiveness evaluation indicators based on PPS, it is not necessary to consider filling them.

In the sensitivity analysis of the main effectiveness evaluation indicators based on FAS, the missing values of the main effectiveness evaluation indicators were not filled.

The missing values of qualitative secondary effectiveness evaluation indicators ORR and DCR were filled by the method of worst observational data carryover (WOCF).

The missing value of the quantitative secondary effectiveness evaluation index DOR was not filled.

Other secondary effectiveness evaluation indicators, such as tumor markers, tumor-specific symptoms, and product ease of use, were not filled.

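### A death after the last radiotherapy fraction and before the month-3 assessment has no assigned primary outcome, and the missing-data rules that would catch it disagree.

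*Protocol*

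**What the plan says.** **Failure rule.** The Note in protocol 3.1.4.1 covers subjects who abort, whatever the cause: "except loss to follow-up) before the end of the last radiation therapy were considered to have disease progression (PD) or were not controlled". The protocol summary and the secondary DCR in 3.1.4.2 set the same time limit. The endpoint is assessed 3 months ± 7 days after the last treatment.

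**Missing month-3 values.**
- Protocol 4.7.2(3) says they can be estimated by worst case.
- SAP 4.3, PPS: "When analyzing the main effectiveness evaluation indicators based on PPS, it is not necessary to consider filling them". Its next sentence says that they are not filled in the FAS sensitivity analysis either.
- SAP 5.4.1, FAS: "missing values of the main effectiveness evaluation indicators were filled by the method of Worst Observational Data Carryover (WOCF"). SAP 4.1 adds unscheduled data to the values that WOCF may use, and SAP 5.6 mentions WOCF conditionally.

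**Sets and denominator.** The PPS requires at least one post-baseline assessment of the primary efficacy measure (SAP section 3). It is the main efficacy population and prevails if the two sets disagree (SAP 5.6). The DCR formula divides by the total number of subjects (protocol 3.1.4.1, SAP 2.1.1). Protocol 4.4 lists missing key endpoint data among the reasons for dropout from the primary analysis.

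**Pass rule.** The lower 95% Clopper-Pearson limit must exceed 80% (protocol 4.5 and 4.7.1, SAP 5.4.1). Separately, any grade 4 or 5 toxicity fails the trial (protocol 4.5).

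**The concern.** A subject who stops for a reason other than loss to follow-up one day before the last fraction is a failure. A subject who dies one day after it has no stated outcome. Such a death is foreseeable: entry needs only an investigator-judged survival above 6 months, ECOG status may be up to 2, and many tumour sites are eligible.

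Death in this window is unlikely to be independent of disease status. Under the SAP the patient can be left out of the PPS, or counted as controlled in the FAS through an earlier SD. Either treatment pushes DCR upward relative to scoring the death as a failure. SAP 5.6 treats agreement between FAS and PPS as support for the result, but if both treatments apply, the two sets share the same error and agree because of it.

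**Working it through.** **1. The plan's own figure.** Inputs: expected rate 95% and target 80% (protocol summary), two-sided alpha 0.05 and power 80% (protocol 4.3). Protocol 4.2.1 states "the test group needs a sample size of at least 42 cases".

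n = [(1.960·√(0.80·0.20) + 0.842·√(0.95·0.05)) / 0.15]² = 41.6, so 42. Then 42/0.90 = 46.7, so 47. Both figures reproduce.

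**2. The rule in counts.** With 47 subjects, the Clopper-Pearson limit exceeds 80% only with 44 or more controlled, so at most 3 failures are allowed (exact power 79.3% at a true 95%). With 42 to 46 subjects the allowance is also 3 failures.

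**3. One death, three scorings.** Take 47 treated, 3 observed PD, 1 death after radiotherapy, and 43 controlled at month 3.

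| Treatment of the death | DCR | Lower 95% limit | Efficacy |
|---|---|---|---|
| Left out (no filling, subject outside the set) | 43/46 = 93.5% | 82.1% | pass |
| WOCF from CR, PR or SD | 44/47 = 93.6% | 82.5% | pass |
| Not controlled (protocol worst case, or unfilled but kept in the denominator) | 43/47 = 91.5% | 79.6% | fail |

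**4. Chance of passing, by number of deaths d among 47, with 95% control in the survivors.**
- Left out: at most 3 failures among 47 − d.
- Scored as failure: at most 3 − d failures among 47 − d.
- WOCF as controlled: at most 3 failures among 47 − d, so the same figures as left out for these d.

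| d | Left out, or WOCF as controlled | Scored as failure | Difference |
|---|---|---|---|
| 1 | 80.3% | 59.4% | 20.9 points |
| 2 | 81.3% | 33.5% | 47.8 points |
| 3 | 82.4% | 10.5% | 71.9 points |
| 4 | 83.3% | 0 | 83.3 points |
| 5 | 84.3% | 0 | 84.3 points |

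**5. Averaging over an assumed mortality q.** The documents give no mortality for this window, so q = 1% to 5% is an assumption. The chance that the efficacy verdict depends on the scoring is the sum over d of Binomial(d; 47, q) times the difference above.
- q = 1%: 0.296·0.209 + 0.069·0.478 + 0.010·0.719 + 0.001·0.833 = about 0.10.
- q = 2%: about 0.21.
- q = 5%: about 0.50.

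The chance of at least one death, 1 − (1 − q)^47, is 38%, 61% and 91%. That is a different and larger quantity.

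**The case against.** A reader might infer that the plan definitely scores a dead patient as controlled, or drops the patient, and so inflates DCR in both populations. The documents do not support that.

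- **FAS.** SAP 4.3 says no filling and SAP 5.4.1 says WOCF, so WOCF is not settled. Where it applies, an earlier PD gives a failure, and a patient with no post-treatment scan has nothing to carry forward. The documents do not say how often the worst earlier reading would be SD.
- **PPS.** If only the month-3 scan counts as a primary efficacy assessment, the patient is outside the set, and protocol 4.4 points that way. If an earlier DCR scan qualifies, the patient is inside, and a denominator of all subjects then makes an unfilled value not controlled in effect.
- **Protocol worst case.** Section 4.7.2(3) names this very missing value. Its permissive wording is weak evidence in a text that reads as a translation. The SAP does not adopt worst case, however, so the conflict remains.
- **Safety criterion.** A death classed as grade 5 toxicity fails the trial whatever DCR shows.
- **Endpoint.** DCR is judged in the irradiated tumour, and survival is followed separately in the long term. Counting deaths from any cause makes the endpoint a composite. That is a choice, not the correction of a miscalculation.
- **Size.** The example in step 3 sits at the boundary by construction.

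All of this narrows the point. What stands is that neither explicit SAP route, no filling or WOCF, assigns failure to a patient who dies after stable scans, while the protocol's worst case would.

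**Conclusion.** The point holds as a gap with conflicting fallback rules. The same patient can be left out, counted as controlled or counted as a failure, depending on which section is followed. An upward bias in DCR is possible under the SAP but not certain.

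Near the boundary a single death decides the efficacy result (82.1% or 82.5% against 79.6%). Over an assumed 1% to 5% mortality in the window, with 95% control among survivors, the efficacy verdict changes with about 10% to 50% probability. The 38% to 91% chance of any death should not be read as the chance of a changed verdict. All these figures come before the safety criterion, so the overall trial verdict is affected mainly by deaths not classed as grade 5 toxicity. Even where the safety criterion fails the trial, the reported DCR would still depend on the unwritten choice.

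**What to change.** 1. In protocol 3.1.4.1 and SAP 2.1.1, 4.3 and 5.4.1, state: *A subject who dies from any cause after the first treatment and before the month-3 assessment is included in FAS and PPS and scored as not controlled at month 3; no WOCF is applied.*
2. Align protocol 4.7.2(3) and SAP 4.3, 5.4.1 and 5.6 to one rule for every other missing month-3 DCR.
3. Amend the PPS definition in protocol 4.9 and SAP section 3 so that these subjects stay in the set.
4. For ORR and the secondary DCR, apply the rule only to time points after the death and keep values observed before it.

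Cost: short text changes before database lock and no new data. DCR may be slightly less favourable, and a death unrelated to the tumour will count against local control. A sensitivity analysis that leaves out clearly unrelated deaths can show how much that matters.
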